## ii. Primary Effectiveness Analysis

Sensitivity, specificity, PPV and NPV of Thermalytix™ as compared to that of standard modalities were reported along with 95% confidence interval.

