## 9. STUDY OBJECTIVES

#### 9.1 PRIMARY OBJECTIVE

- To evaluate the effectiveness of Thermalytix™ for breast cancer screening as compared to standard screening modalities for breast cancer
- 2. To correlate the results of Thermalytix™ with digital mammography for screening diagnostics on patients walking in for health check as measured by:
  - Sensitivity of Thermalytix™ as compared to sensitivity of mammography
  - Specificity of Thermalytix™ as compared to specificity of mammography

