### 10. INVESTIGATIONAL PLAN

#### 10.1 OVERALL STUDY DESIGN AND PLAN

This was a prospective, comparative study to evaluate the effectiveness of Thermalytix™ when compared to the standard screening modalities in females of age 18 years and above. The study was initiated after appropriate clearance from the ethics committee.

The study visits included a screening visit (Visit 1) followed by visits at Day 2-5 (Visit 2), Day 6-10 (Visit 3) and Day 10-14 (Visit 4):

- 1. The Visit 1 procedures included informed consent process, collection of information regarding current complaints, past medical history and treatment, family history, physical examination, record of risk factors, followed by Thermalytix™ procedures, and mammography as part of routine screening for all woman enrolled in the study. The Mammography machine used was (GE Dmr Plus analog Mammography and Prodigy). Thermalytix employed Algorithm ver 3.0.
- 2. The Visit 2 procedures were based on the results of Thermalytix™ and mammography and were conducted only for the women who had an inconclusive mammography report or who were reported as positive by either or both Thermalytix™ and mammography.
  - If mammography was inconclusive, a confirmatory test which included USG, or MRI scan was recommended by the clinician. The breast ultrasound (USG) was done using Samsung RS85 and MRI was performed on GE 3.0T.
  - If either or both Thermalytix™ and mammography reported the case as positive, a confirmatory test which included USG, MRI, or PET scan was recommended by the clinician. If any of the three tests identified a suspicious lesion, FNAC/biopsy was recommended in the same or follow-up visit.

16 Sep 2020 Confidential Page 21 of 53

- 3. The Visit 3 procedures included FNAC/biopsy and related laboratory work-up. Women underwent MRI guided biopsy in cases where results were positive by MRI.
- 4. The final visit or the Visit 4 was done by telephonic contact and all the procedures were completed for all the subjects enrolled into the study.

Women reported as negative for cancer by both tests (Thermalytix™ and mammography) would complete visits 1 and 4 only. Whereas positive cases and suspected cancer cases completed all visits as applicable. The patients were expected to go through the entire screening process within a duration of 2 weeks from enrollment on the study.

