## 10.2 DISCUSSION OF STUDY DESIGN

The prospective and comparative nature of the study design was the most appropriate approach to evaluate the objectives of the study because the specificity, sensitivity, and accuracy of Thermalytix™ would be beneficial in clinical practice.

This study was done as a comparison to the standard method of mammography. The sensitivity of Thermalytix™ (an automated thermographic screening algorithm developed by Niramai) was compared to the sensitivity of mammography and to study how Thermalytix™ can complement the standard modalities in breast cancer screening in future.

16 Sep 2020 Confidential Page 22 of 53

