# 10.7 STATISTICAL METHODS PLANNED IN THE PROTOCOL AND DETERMINATION OF THE SAMPLE SIZE

#### 10.7.1 Statistical and Analytical Plans

Analysis of the data was performed by the Biostatistics and Statistical Programming team of Statiza Statistical Services. All statistical analyses were performed using R Software version 3.5.0 and SAS® Version 9.4 or higher [SAS Institute Inc., USA].

The following standard descriptive summaries were presented:

The continuous data was summarized using the number of observations (n), arithmetic mean (mean), standard deviation (SD), median, minimum value (min), and maximum value (max). The categorical variables were summarized using the frequency count (n) and percentage (%) for each possible value. The frequencies were presented up to 0 decimal places and percentage up to 2 decimal places.

Thermalytix™ and standard modalities were evaluated using following measures of validity:

- Sensitivity The probability of correctly identifying a true case of malignancy
- Specificity The probability of correctly identifying a true case of non-malignancy (normal or benign)
- Positive Predictive Value (PPV) The probability that a labelled positive was a true case of malignancy
- Negative Predictive Value (NPV) The probability that a labelled negative was a true case of non-malignancy

All the methods of validity were computed for Thermalytix™ along with their 95% CI.

16 Sep 2020 Confidential Page 29 of 53

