## i. Subject Population

FAS Population: All enrolled subjects who underwent thermography (AI-based Thermalytix™) and mammography and satisfied inclusion criteria and rest of the protocol requirement, were considered in Full Analysis set (FAS). All statistical analyses were performed considering FAS population.

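### The primary objective compares Thermalytix with mammography in the same women, but section 10.7 specifies no interval for the between-test difference that uses the pairing

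*Combined protocol and SAP*

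**What the plan says.** Section 9.1 makes the comparison a primary objective: sensitivity against that of mammography, and specificity "as compared to specificity of mammography". Section 10.2 repeats it for sensitivity, which "was compared to the sensitivity of mammography".

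The design is paired. Section 10.1 gives every enrolled woman both tests at Visit 1, and section 10.7.1 i defines the full analysis set as "All enrolled subjects who underwent thermography (AI-based Thermalytix™) and mammography and satisfied inclusion criteria", together with the remaining protocol requirements.

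On analysis, section 10.7.1 defines sensitivity, specificity, PPV and NPV and states: "All the methods of validity were computed for Thermalytix™ along with their 95% CI". Section 10.7.1 ii says that these measures for Thermalytix "as compared to that of standard modalities were reported along with 95% confidence interval". Section 10.7.2 sizes the study on the width of one Clopper-Pearson interval for one sensitivity. Section 10.7 names no difference or ratio, paired interval, test, hypothesis or margin. Section 10.8.2 reports no changes to the analyses.

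Verification depended on the test results. Women negative on both tests "would complete visits 1 and 4 only". For women positive on either or both, "a confirmatory test which included USG, MRI, or PET scan was recommended by the clinician". Visit 2 also took in "women who had an inconclusive mammography report".

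**The concern.** The primary question is a contrast: does Thermalytix detect and exclude cancer as well as, better than or worse than mammography in the same women? Read naturally, section 10.7 answers a different question, namely how precisely each test's accuracy is estimated on its own.

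Two separate intervals do not settle the contrast. They can overlap when the interval for the difference excludes zero, and a reader may take overlap as a sign that the tests perform alike. They also discard the within-woman pairing, which narrows the interval for the difference when the two tests' results are positively correlated. Because no estimand or method is named, two analysts could report different comparisons from the same data.

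The point is limited to mammography. It is the only standard modality that every woman in the analysis set has; ultrasound, MRI and PET were done only in some.

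**Working it through.** **Inputs from the documents.** Prevalence 4%, sensitivity 80%, planned sample 300, stated width 0.487 and analysed sample 459 (section 10.7.2); mammography sensitivity 64% to 90% (section 8).

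**Assumptions.** The specificities (85 v 90%, 90 v 93%) and the correlations between the tests' results (phi = 0, 0.2, 0.4) are not in the documents. The 4% is a lifetime figure for breast cancer and other breast abnormalities, not a malignancy rate. The case counts below are therefore assumptions, and the true number of cancers may be lower.

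**1. The plan's own figure.** Expected cases: 300 x 0.04 = 12; expected positives: 0.80 x 12 = 9.6. The Clopper-Pearson limits are the 2.5% quantile of Beta(x, n - x + 1) and the 97.5% quantile of Beta(x + 1, n - x). With x = 9.6 and n = 12 they are 0.4796 and 0.9670, a width of 0.487. The stated width reproduces, and it belongs to one test's sensitivity, not to a comparison.

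**2. Denominators.** 459 x 0.04 = 18.4, about 18 cancers, leaving 459 - 18 = 441 non-malignant women. With fewer cancers, 441 rises towards 459, so the specificity figures hardly move.

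**3. Separate exact intervals, 85 v 90%.** 375/441 gives 81.4 to 88.2%; 397/441 gives 86.8 to 92.7%. They overlap.

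**4. Interval for the difference (Thermalytix minus mammography).** With q = 1 - p,

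SE² = [p1q1 + p2q2 - 2·phi·√(p1q1p2q2)] / n, and the 95% CI is d ± 1.96·SE.

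For 85 v 90%, p1q1 = 0.1275, p2q2 = 0.0900 and √(p1q1p2q2) = 0.1071. At phi = 0.4, SE = √[(0.2175 - 0.0857)/441] = 0.0173.

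| Specificities | phi | SE | 95% CI, points |
|---|---|---|---|
| 85 v 90% | 0 | 0.0222 | -9.3 to -0.6 |
| 85 v 90% | 0.2 | 0.0199 | -8.9 to -1.1 |
| 85 v 90% | 0.4 | 0.0173 | -8.4 to -1.6 |
| 90 v 93% | 0 | 0.0188 | -6.7 to 0.7 |
| 90 v 93% | 0.2 | 0.0168 | -6.3 to 0.3 |
| 90 v 93% | 0.4 | 0.0146 | -5.9 to -0.1 |

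The first row uses the whole-number counts 375 and 397; the formula with 0.85 and 0.90 gives -9.35 to -0.65. For 85 v 90% the widths are 8.7, 7.8 and 6.8 points, so pairing narrows the interval by 10% and 22%.

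**5. Check with the paired score (Tango) interval on whole-number cells.** At 85 v 90%: -9.0 to -1.1 (phi 0.2) and -8.6 to -1.6 (phi 0.4). At 90 v 93%: -6.4 to 0.4 (phi 0.2) and -6.2 to -0.3 (phi 0.4). The readings are the same.

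**6. Sensitivity.** Exact McNemar needs at least six discordant cancers, all in one direction, for two-sided p < 0.05: 2 x 0.5⁶ = 0.031, while 2 x 0.5⁵ = 0.0625. Power by full enumeration, Thermalytix at 80%:

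| Mammography | Cancers | phi 0 | phi 0.2 | phi 0.4 |
|---|---|---|---|---|
| 64% | 12 | 3.6% | 2.7% | 1.7% |
| 64% | 18 | 9.1% | 9.1% | 8.3% |
| 90% | 12 | 0.7% | 0.4% | 0.2% |
| 90% | 18 | 3.1% | 2.4% | 1.6% |

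The approximate width of a paired interval at zero difference is 3.92·√(psi/n), where psi is the discordant proportion. For psi from 0.1 to 0.4 it is 0.36 to 0.72 with 12 cancers and 0.29 to 0.58 with 18.

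**7. Inconclusive mammograms.** Among 441 women, every 10 such mammograms move mammography's specificity by 10/441 = 2.3 points, depending on how they are counted.

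**The case against.** The strongest reply has four parts.

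- **Wording.** Section 10.7.1 ii can be read as placing the interval on the comparison itself. That reading is possible, but the sentence still names no estimand, no method and no allowance for pairing, so the gap in the specification remains.
- **What was actually done.** A reader might infer that no paired comparison was ever computed. The documents do not support that. The sections available here describe methods; the results tables are not among them. The point is that section 10.7 does not specify the analysis, not that it was left undone.
- **Design philosophy.** The study is sized on precision, states no hypothesis or margin, and may legitimately present estimates with intervals. This stands: the lack of a significance test is not an error. It does not answer the point, because a precision-based study with a comparative objective still needs an interval for the comparison.
- **Modest consequences.** In the 85 v 90% example even the unpaired interval for the difference excludes zero, so pairing changes no conclusion there. At 90 v 93% it changes the reading only at a correlation of 0.4, and narrowly. At correlation 0 it gains nothing. For sensitivity, the measure the study was sized on, no method rescues so few cancers. All of this stands, and it limits the size of the point.

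**Conclusion.** The point holds as an omission in section 10.7 that should be repaired: a primary comparative objective on paired data has no specified interval for the difference. The practical value lies mainly in specificity. There, a difference interval can resolve what two overlapping intervals leave open, and pairing narrows it by 10 to 22% at assumed correlations of 0.2 to 0.4. Those figures rest on assumed specificities and correlations and on about 441 non-malignant women.

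For sensitivity the benefit is honesty about imprecision rather than a usable answer. Power is 0.2 to 9% with 12 to 18 cancers, and that count borrows a lifetime figure that also covers other abnormalities.

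Two stronger conclusions are not supported. The documents do not show that the reported accuracy figures are wrong, and they do not show that ignoring the pairing reversed any result.

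**What to change.** Report the Thermalytix by mammography 2x2 table separately for malignant and non-malignant women. From these, give the paired difference (Thermalytix minus mammography) in both sensitivity and specificity, each with a paired score 95% interval such as Tango's. Exact McNemar may be added as a supplement. Disclose all of this as added analyses in section 10.8.2, which at present reports no changes.

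Alongside the results, state:

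- the number of inconclusive mammograms and how they are counted;
- that the sensitivity comparison is very imprecise;
- that overlapping intervals or a non-significant test do not show equivalence;
- that both contrasts, specificity included, depend on the verification of test-positive women, since women negative on both tests had no planned confirmatory test.

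The cost is a few lines of analysis on data already held, plus a sensitivity interval that will be visibly wide. It does not recover cancers missed in women who were never verified.

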## iii. Secondary Effectiveness Analyses

Influence of patient characteristics such as age group, menopause status and breast density on diagnostic accuracy (sensitivity, specificity, PPV and NPV) of Thermalytix™ as compared to that of standard modalities were reported along with 95% confidence interval.

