## 8. INTRODUCTION

Breast cancer has the highest incidence among cancers in women worldwide [1]. An estimated 2.08 million women worldwide had been diagnosed with breast cancer in 2018, and in a five-year prevalence period, 6.8 million women have breast cancer [1]. In India, the incidence is 162 thousand, with a five-year prevalence is 405 thousand in 2018 [1]. Breast cancer is curable if diagnosed in the early stage. Hence, screening is important for early detection. Mammography is the current gold standard for breast cancer screening. However, mammography is less sensitive on younger women due to denser tissue. Further, the radiation effects due to the X-rays may be harmful enough to cause cancer in younger women [2]. The reported sensitivity of mammography ranges between 64% in extremely dense breast tissue to 90% in less dense tissue [2].

The feasibility of using thermography as an alternative breast imaging modality to current modalities is being evaluated with a goal towards screening of the patients to detect early breast cancer. Niramai has pioneered an advanced method of screening for breast cancer by enhancing thermography with machine intelligence. This combination of thermography and computer aided diagnostics is called Thermalytix™. Patented Niramai's Thermalytix™ solution uses machine learning (advanced data analytics and an upcoming research theme in Computer Science) consisting of probabilistic mathematical modelling of a decision process and statistical analysis of historic data to predict whether the subject belongs to malignant class or benign/normal Class.

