#### 9.2 **SECONDARY OBJECTIVES**

- Influence of patient characteristics on diagnostic accuracy of Thermalytix™.
  Patient characteristics will include:
  - Age
  - Lesion type
  - Pathologic diagnosis
  - Menopausal and hormonal status
  - Breast density
  - Family history
- 2. Recommend how Thermalytix™ can be used to complement standard breast cancer screening procedure.

16 Sep 2020 Confidential Page 20 of 53

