#### 10.4 **STUDY PROCEDURES**

All the enrolled subjects underwent thermal imaging (to conduct Thermalytix™) by a technician trained by the sponsor in strict compliance to the procedure (Appendix I of the

16 Sep 2020 Confidential Page 23 of 53

study protocol) using thermal camera. The thermal images were interpreted by the AI-based algorithm 'Thermalytix™'. The Thermalytix™ report and the standard screening reports were collated by the study coordinator and entered in the CRFs.

The results of Thermalytix™ and mammography were correlated, and the correlation results were analyzed by PI. If the reports of the two tests correlated, a secondary test was not mandated. In case of inconclusive reports from standard modality, subjects underwent confirmatory breast USG/MRI/PET scan as determined by the PI. In case Thermalytix™ identified lesions suspicious of malignancy and mammography did not identify the lesion, to resolve the discrepancy between the two tests, the subject underwent confirmatory breast USG/MRI/PET scan as determined by the PI. USG-guided biopsy was the confirmatory test for cases reported as positive by imaging modalities. MRI-guided biopsy was performed in cases where results were positive for malignancy by MRI. When all the results were received and final diagnosis were confirmed, subjects were contacted telephonically to complete the end of trial procedure and their treatment course was decided by the treating doctor.

Study Coordinator transcribed all the data in the CRF. Data from individual CRFs were entered by the Study Coordinator in the excel spreadsheet and sent to the Data Management group for analysis.

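### Thermalytix sensitivity by density or age is measured only among cancers that a test flagged, so differences between strata are not evidence of a density or age effect

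*Combined protocol and SAP*

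**What the plan says.** Secondary objective 1 (section 9.2) is "Influence of patient characteristics on diagnostic accuracy of Thermalytix™", and its list of characteristics includes age, menopausal status and breast density. Section 10.7.1 iii answers it with "Influence of patient characteristics such as age group, menopause status and breast density on diagnostic accuracy": sensitivity, specificity, PPV and NPV in each group, set against the standard modalities, with 95% confidence intervals.

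The work-up rule decides which cancers can be counted. In section 10.1, Visit 2 procedures were "conducted only for the women who had an inconclusive mammography report or who were reported as positive by either or both" of the tests, while women negative on both "would complete visits 1 and 4 only", the latter being a telephone contact. Section 10.4 adds: "If the reports of the two tests correlated, a secondary test was not mandated". Nothing later would reveal a cancer that both tests missed: "The patients were expected to go through the entire screening process within a duration of 2 weeks from enrollment on the study".

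The Introduction says that mammography's sensitivity "ranges between 64% in extremely dense breast tissue to 90% in less dense tissue", and that it is lower in younger women. Section 10.7.1 mentions neither partial verification nor a correction for it.

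**The concern.** A Thermalytix miss enters a stratum's denominator only if mammography flags the same woman, as positive or inconclusive. Where mammography is less sensitive, more Thermalytix misses drop out and the reported Thermalytix sensitivity rises further above the truth. Because mammography's sensitivity varies with density, this inflation varies too. The stratum figures can therefore differ when Thermalytix performs identically in all of them.

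Dense breasts and younger women are the groups in which the Introduction describes mammography as weak. An apparent Thermalytix advantage there could be read as an answer to secondary objective 1, and could carry into secondary objective 2, on how the device should complement screening.

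**Working it through.** **Inputs.** Mammography sensitivity m = 0.64 (extremely dense) and 0.90 (less dense), from the Introduction. Thermalytix sensitivity t = 0.80, the planning value in section 10.7.2, here assumed equal in both strata. Prevalence 4%, with 300 women planned and 459 analysed (section 10.7.2). The documents do not give the dependence between the tests or the rate of inconclusive mammograms, so both are varied.

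**1. The plan's own figure.** 300 × 0.04 = 12 cases. The Clopper-Pearson 95% interval at 80% of 12 (x = 9.6) is 0.480 to 0.967, width 0.487. The stated width reproduces.

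**2. Base case.** If d is the share of cancers negative on both tests, apparent sensitivity = t / (1 − d). With tests independent given cancer, d = (1 − t)(1 − m).
- Extremely dense: d = 0.20 × 0.36 = 0.072; 0.80 / 0.928 = 86.2%.
- Less dense: d = 0.20 × 0.10 = 0.020; 0.80 / 0.980 = 81.6%.
- False gap: 4.6 points. With every woman verified, both would read 80% and the gap would be 0.

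The result is the same whether double-negative women are counted as non-malignant or left out of the sensitivity denominator.

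**3. Other true sensitivities, still independent.** The gap is 7.6 points at t = 0.60, 6.3 at 0.70 and 2.5 at 0.90.

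**4. Tests that tend to miss the same cancers (t = 0.80).** Add a fraction of the maximum covariance, min(1 − t, 1 − m) − (1 − t)(1 − m), to d. The maximum is 0.128 in dense and 0.080 in less dense tissue.
- 25%: d = 0.104 and 0.040; 89.3% against 83.3%; gap 6.0.
- 50%: d = 0.136 and 0.060; 92.6% against 85.1%; gap 7.5.

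Dependence does not always widen the gap: at t = 0.90 it falls from 2.5 to 1.9 and 1.3 points.

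**5. Inconclusive mammograms (t = 0.80, independent).** If a share f of mammography-missed cancers is read as inconclusive and so worked up, d becomes d(1 − f).

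| f | Same f in both strata | f in dense stratum only |
|---|---|---|
| 0.25 | +3.3 | +2.9 |
| 0.50 | +2.2 | +1.4 |
| 0.72 | +1.2 | about 0 |
| 1.00 | 0 | −1.6 |

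**6. Thermalytix against mammography within a stratum.** Both apparent sensitivities share the divisor 1 − d, so their ratio is unaffected: 0.80/0.64 = 1.25 in dense and 0.80/0.90 = 0.889 in less dense tissue. The base-case difference is only slightly inflated: 0.172 against a true 0.160, and −0.102 against −0.100.

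**7. Precision.** 459 × 0.04 is about 18 cases. With an assumed even split of 9 per stratum, the standard error of the gap is √[(0.862 × 0.138 + 0.816 × 0.184)/9] = 0.173, a 95% half-width of about 34 points. The expected number of double-negative cancers is 9 × 0.072 + 9 × 0.020 = 0.65 + 0.18, under one in total.

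**8. Restricting to mammography-positive cancers (t = 0.80).** The share of these that are Thermalytix-positive is 80% in both strata under independence, but not under dependence.
- 25%: 0.544/0.64 = 85.0% against 0.74/0.90 = 82.2%; gap 2.8.
- 50%: 0.576/0.64 = 90.0% against 0.76/0.90 = 84.4%; gap 5.6.

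**The case against.** The strongest reply is that the comparison section 10.7.1 iii actually states is Thermalytix against standard modalities within each group, which step 6 shows to be almost undistorted. No between-stratum test, difference or interval is planned. That stands: a reader might infer that the plan builds in a biased between-stratum interval, and it does not. What remains is that objective 1 concerns Thermalytix's own accuracy, and stratum sensitivities offered as showing influence will be compared with each other.

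A reader might also infer that the distortion must favour the device in dense breasts and in younger women. The documents do not support that as a certainty. Inconclusive mammograms also lead to work-up, and if they recover enough missed cancers in dense breasts the gap disappears or reverses (step 5). The 64% and 90% are the ends of a reported range and the plan does not define its density strata, so coarser strata would normally give a smaller contrast in m. For age the Introduction gives a direction and no figure; for menopause it gives neither.

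The practical weight is modest. Sampling error is several times the bias, and the 4% prevalence covers other breast abnormalities as well as cancer, so there may be fewer cancers than assumed here.

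Finally, all this follows from partial verification, and a remedy for the primary analysis would cover much of it. A single caveat on the overall level would not be enough, because the inflation differs by stratum.

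**Conclusion.** The point holds as a limit on interpretation. The planned stratum sensitivities describe cancers flagged by either test or by an inconclusive mammogram. On the documents' own figures, a constant true sensitivity of 80% with conditionally independent tests would show a false density gap of about 4.6 points at the extremes of the quoted range. It would be 6.0 to 7.5 points at 25% to 50% of maximum positive dependence, and smaller, zero or as low as −1.6 points depending on an inconclusive rate that the documents do not give. For age only a direction is supported, and for menopause nothing is.

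The consequence is a biased estimate that may be over-read, not a significant false finding: about 12 to 18 expected cases leave a 95% half-width of about 34 points for the gap. It is also tempting to conclude that restricting to mammography-flagged cancers cures the problem. Step 8 shows that it does so only under conditional independence.

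**What to change.** In section 10.7.1 iii:

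1. Label the stratum sensitivities of both Thermalytix and mammography as 'among cancers flagged by either test', noting that inconclusive mammograms also count as flagged. State that differences between strata in this absolute sensitivity will not be used as evidence of a density or age effect.
2. Make the within-stratum comparison with mammography the ratio of confirmed cancers detected by each test, with a 95% CI that respects the pairing. State whether an inconclusive mammogram counts as a detection. Unverified double-negatives do not distort this ratio, provided that work-up confirms the cancers that are flagged. A ratio that differs between strata may reflect a change in mammography, so it speaks to relative performance only.
3. Add a sensitivity analysis by stratum. With a Thermalytix-positive cancers among c confirmed cancers, report a/(c + k) over a range of k missed cancers among double-negative women. Include the values implied by independence and by positive dependence, k = c × d/(1 − d), with d from steps 2 and 4.
4. If the share Thermalytix-positive among mammography-flagged cancers is shown, keep it as a supplementary row with its conditional-independence assumption stated, and base no density claim on it.

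The cost is some wording and a few extra table rows from data already held, with no new patients or procedures. The downside is wider stated uncertainty and a more limited secondary conclusion.

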#### 10.3 **SELECTION OF STUDY POPULATION**

### 10.3.1 Inclusion Criteria

Subjects were eligible for participation in the study if they met the following criteria:

- 1. Female subjects equal to and above 18 years
- 2. Subjects who are willing to give written informed consent for study participation
- 3. Subjects who are ready to comply with the study related visits and procedures

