# 10.7.2 Determination of Sample Size

The sample size was calculated with two-sided 95% confidence interval (CI) for a sample sensitivity and target width of 0.5 using Clopper-Pearson Interval (Exact) Method. The prevalence of breast cancer and other breast abnormalities in Indian women during their lifetime was assumed to be 4% (1 in 25 were expected to have a breast abnormality in their lifetime in India). A sample size of 300 screening patients allows estimating the true prevalence by means of an exact 95% confidence interval with width of 0.487 percent points when the sample sensitivity was assumed to be 80%. Considering exclusions from data analysis due to multiple visits needed, over 600 women were recruited. Eventually, data of 459 women could be used for statistical analysis as they satisfied inclusion criteria and adhered to the study protocol.

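### Age is a secondary-objective characteristic, but the only form of age the analysis names is age group, with no use of band order or of age in years, which weakens detection of a moderate age gradient in specificity

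*Combined protocol and SAP*

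**What the plan says.** Section 9.2 sets the secondary objective as "Influence of patient characteristics on diagnostic accuracy of Thermalytix™" and puts age first in the list of characteristics. It does not say whether age is to be used in years or in bands.

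Section 10.7.1 iii is the only analysis text supplied for that objective. It reads "Influence of patient characteristics such as age group, menopause status and breast density on diagnostic accuracy", and the output is sensitivity, specificity, PPV and NPV "of Thermalytix™ as compared to that of standard modalities were reported along with 95% confidence interval". It gives no number of groups, boundaries, model, trend or test for an age effect.

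On the population, section 10.3.1 admits "Female subjects equal to and above 18 years" with no upper limit. The Introduction says that "mammography is less sensitive on younger women due to denser tissue", so age bears on the reason for studying the device. Specificity is defined in 10.7.1 as "The probability of correctly identifying a true case of non-malignancy (normal or benign"), so each non-malignant woman contributes a yes/no outcome.

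**The concern.** Estimating accuracy separately in each age band treats all women in a band as the same age and the bands as unrelated categories. If specificity changes gradually with age, both the differences within a band and the order of the bands are discarded. With the boundaries unstated, a reader also cannot tell how far the pattern depends on where they fall.

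Specificity is where this matters most, because it is the measure with enough women to estimate an age effect. What is at stake is a secondary objective: a moderate gradient could look like overlapping intervals and be read as no influence of age. The primary analysis and the sample size are not affected.

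**Working it through.** **The plan's own figure.** Section 10.7.2 uses a "target width of 0.5 using Clopper-Pearson Interval (Exact) Method". With 300 × 0.04 = 12 cases and 80% sensitivity (x = 9.6), the Clopper-Pearson limits are 0.480 and 0.967. The width is 0.487, as stated. This figure concerns overall sensitivity; the supplied text gives no figure for the age analysis.

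**Inputs from the documents.** 459 women analysed and 4% assumed prevalence (10.7.2). Cancers: 459 × 0.04 ≈ 18. Non-malignant: 459 − 18 = 441. The 4% is described there as a lifetime figure for cancer and other abnormalities, so the split is itself an assumption.

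**Inputs assumed, because the documents give none.** Age about normal, mean 45, SD 12; specificity linear in age on the logit scale, 85% at −1 SD and 92% at +1 SD; two-sided 5% test.

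**Step 1: information kept by grouping.** For a linear effect, the share kept is the between-group variance of age divided by its total variance. For two equal groups of a normal variable this is 2/π = 0.637.

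| Grouping | Lost, normal age | Lost, uniform age |
|---|---|---|
| 2 equal groups | 36% | 25% |
| 3 equal | 21% | 11% |
| 4 equal | 14% | 6% |
| 5 equal | 10% | 4% |
| 6 equal | 8% | 3% |
| 2 groups, 30/70 | 42% | – |
| 2 groups, 20/80 | 51% | – |

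In terms of precision, the interval for a linear age effect widens by 1/√(share kept): 1/√0.637 = 1.25 for a median split, 1/√0.793 = 1.12 for three equal groups. For three or more groups these figures require the order of the bands to be used.

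**Step 2: power by formula.** The log odds ratio per SD is β = [logit(0.92) − logit(0.85)]/2 = (2.442 − 1.735)/2 = 0.354, an odds ratio of 1.42. At the midpoint, specificity is 0.890 and p(1 − p) = 0.098. The noncentrality is n·p(1 − p)·β² = 441 × 0.0981 × 0.354² ≈ 5.42.

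- Linear age, 1 df: 5.42 gives power 64%.
- Median split, 1 df: 5.42 × 0.637 = 3.45 gives 46%.
- Three equal unordered groups, 2 df: 5.42 × 0.793 = 4.30 gives 44%.
- Four equal unordered groups, 3 df: 5.42 × 0.861 = 4.66 gives 41%.

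**Step 3: power by simulation in the same scenario.**

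| Use of age | Power |
|---|---|
| One linear term in years | 62% |
| 3-knot restricted cubic spline, 2 df | 51% |
| Trend across ordered bands | 52-54% |
| Two groups | 40-45% |
| Three equal groups, unordered | 42% |
| Four bands, unordered | 38% |

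Repeat runs put the linear term at 59-64%, so about 60% is a fair summary. Adding unordered bands does not help, because the extra degrees of freedom offset the information regained.

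**Step 4: other effect sizes.** With two equal age groups (220 and 221 women), power is 99% for 75% versus 90%, 84% for 80% versus 90%, and 28% for 80% versus 85%. Large differences are found under grouping, and small ones are hard to find. The cost falls on effects in between: at average specificity 85% and an odds ratio of 1.5 per SD, power is 86% with linear age, 68% with two groups and 77% with a three-group trend.

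**Step 5: sensitivity.** With 18 cancers in two equal age groups, 7 of 9 detected has an exact 95% interval of 0.400 to 0.972. With three groups, 5 of 6 gives 0.359 to 0.996. No coding of age makes this more than descriptive.

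**The case against.** Accuracy by age band with confidence intervals is a common and readable way to answer a descriptive secondary objective. The plan states no test, significance level or decision rule for age, so power describes a procedure it does not contain. That stands: the power figures are a yardstick for how well each use of age can show a gradient, not a property of a planned test.

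Four stronger readings are tempting, and the documents do not support them.

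- *Age will be analysed only in groups.* The text says such as age group, which is an example and does not rule out age in years. Sections 10.5 and 10.6 are not in the supplied text, and boundaries could be given there.
- *About a third of the age information is discarded.* That holds only for a near-median split of roughly normal age into two groups. The number of groups is not stated.
- *Real age effects will go undetected.* Large ones are found with two groups, and even the linear term would miss the example gradient about 40% of the time.
- *Boundaries might be chosen to suit the result.* Picking the best of five cut-points would raise the false-positive rate to about 16-18%, but nothing suggests that this was done.

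Two further points limit the gain. The simulated gradient is exactly linear on the logit scale, which favours the linear term; a spline as the main test (51%) does no better than a trend across ordered bands (52-54%). And the Introduction's remark on age concerns mammography's sensitivity. It shows that age matters to the rationale, but it is not evidence of a gradient in Thermalytix specificity.

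**Conclusion.** The point holds in a limited form. The objective concerns age; the only form of age named in its analysis is age group, with undefined bands, separate estimates and no use of their order. Under the assumed inputs, power for a moderate gradient in specificity is about 60% with a linear age term, against about 40-45% with two groups and 38-42% with three or four unordered groups. Using the order of the bands recovers part of the gap.

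The size depends on the assumed age distribution, specificity, effect and number of groups, and on 4% malignancy in 459 women. The direction of the loss depends only on the effect being roughly monotone in age. This is a worthwhile low-cost improvement to a secondary analysis, not a flaw in the primary one.

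**What to change.** In section 10.7.1 iii:

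1. Keep the age-group table, state its boundaries, and say whether they were set before results were seen.
2. Among women with a non-malignant final diagnosis, add a logistic regression of a negative result on age in years, fitted for Thermalytix and for mammography. Make one linear term the main estimate, with a 3-knot restricted cubic spline (10th, 50th and 90th percentiles) only as a check on shape. Report the age odds ratio and the fitted specificity with 95% confidence intervals at fixed ages, for example 30, 40, 50, 60 and 70.
3. For sensitivity, fit a single linear age term with Firth penalisation and label it descriptive.

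The cost is a few sentences and a short model run in the software already named, using each woman's age; no extra women or procedures are needed and the planned table stays. The main estimate relies on linearity on the logit scale, which the spline checks. The documents are written in the past tense, with 459 women already selected for analysis, so the model should be labelled supportive, or post hoc if it is added after results are known.
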